	3rd.	Hold suspected drug. Follow until toxicity ≤ Grade 2. Resume the held drug at ONE dose level below current dose. Dose re-escalation of the drug to prior dose is permitted in accordance with the dose-escalation guidelines outlined below Patients who are experiencing ongoing dose delays >8 weeks due to unresolved grade ≥3 adverse events should be taken off treatment.
	4th time	Discontinue therapy

5.4.3 IO-agent (avelumab and PF-04518600) dose delay/interruption for immune-oncology drug-related AEs, clinically significant in the opinion of the investigator

All IO-agent/s administration should be delayed for the following drug-related AEs, clinically significant in the opinion of the investigator:

- Any Grade ≥ 2 non-skin AE, except that
 - Grade 2 fatigue or laboratory abnormalities do not require delay, however patients with ALT or AST > 3 and up to 5 x ULN or total bilirubin greater > 2.0 mg/dL and up to 3 x ULN or creatinine > 2.0 mg/dL and up to 3 x ULN should have avelumab treatment withheld.

All IO agent/s administration should be delayed for the following drug-related AEs, clinically significant in the opinion of the investigator:

- Any Grade 3 skin AE, or Grade 3 laboratory abnormality, with the following exceptions:
 - Grade 3 lymphopenia or leukopenia does not require dose delay.
 - However, patients with drug-related ALT or AST > 5 x ULN or total bilirubin greater > 3 x ULN or creatinine > 3 x ULN should have avelumab treatment interrupted.
 - Any AE, laboratory abnormality, or intercurrent illness, which in the judgment of the investigator, warrants delaying the dose of study medication.
 - IO-agent dose reductions are not permitted in this study (only dose delays when indicated).

Subjects may resume treatment with study drug when the drug-related AE(s) resolve to Grade ≤ 1 or baseline value, with the following exceptions:

- Subjects may resume treatment in the presence of Grade 2 drug-related fatigue
- Subjects who have not experienced a Grade 3 drug-related skin AE may resume treatment in the presence of Grade 2 skin toxicity
- Drug-related pulmonary toxicity, diarrhea, or colitis, must have resolved to baseline or at least \leq grade 1 before treatment is resumed
- Drug-related endocrinopathies adequately controlled may resume treatment

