If the criteria to resume treatment are met, the subject should restart treatment at the next scheduled time point per protocol. However, if the treatment is delayed past the next scheduled time point per protocol, the next scheduled time point will be delayed until dosing resumes. Patients who receive combination therapy in whom continuation of the non-IO agent(s) (e.g. azacitidine, GO and/or venetoclax) is considered to be inadequate, or inappropriate (e.g., because of pancytopenia or other considered related severe toxicity) can discontinue these agents and continue with IO-agent only.

Patients who are experiencing ongoing dose delays > 8 weeks due to unresolved grade ≥ 3 adverse events should be taken off treatment, except as specified in discontinuation section.

5.4.4 IO-agent Discontinuation Criteria: The following clinically significant, drug-related ADRs require permanent treatment discontinuation of any IO=agent/s:

---Any Grade 4 drug-related AEs require treatment discontinuation with IO-agent/s except for single laboratory values out of normal range that are unlikely related to study treatment as assessed by the Investigator, do not have any clinical correlate, and resolve within 7 days with adequate medical management

---Any Grade 3 drug-related AEs require treatment discontinuation with IO-agent/s except for any of the following:

- Transient (\leq 6 hours) Grade 3 flu-like symptoms or fever, which is controlled with medical management
- Transient (\leq 24 hours) Grade 3 fatigue, local reactions, headache, nausea, emesis that resolves to Grade \leq 1
- Single laboratory values out of normal range (excluding Grade \geq 3 liver function test increase) that are unlikely related to study treatment according to the Investigator, do not have any clinical correlate, and resolve to Grade \leq 1 within 7 days with adequate medical management
- Tumor flare phenomenon defined as local pain, irritation, or rash localized at sites of known or suspected tumor
- Change in ECOG PS to \geq 3 that does not resolve to \leq 2 within 14 days (infusions should not be given on the following cycle, if the ECOG PS is \geq 3 on the day of study drug administration)

Any Grade 2 drug-related AEs should be managed as follows:

- If a Grade 2 AE resolves to Grade \leq 1 by the last day of the current cycle, treatment may continue.

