- If a Grade 2 AE does not resolve to Grade \leq 1 by the last day of the current cycle, infusions should not be given on the following cycle. If at the end of the following cycle the event has not resolved to Grade 1, the subject should permanently discontinue treatment with IO-agent/s (except for hormone insufficiencies, that can be managed by replacement therapy; for these hormone insufficiencies, up to 2 subsequent doses may be omitted).
- Upon the second occurrence of the same Grade 2 AE (except for hormone insufficiencies that can be managed by replacement therapy) in the same subject, treatment with the IO-agent/s has to be permanently discontinued unless the patient is deriving clinical benefit in which case the agent may be continued after discussion with the PI of potential risk/benefit ratio and documentation of this discussion in the patient's medical record.
- Infusion-related reactions, hypersensitivity reactions (Grades 1 to 4), and tumor lysis syndrome should be handled according to guidelines provided.
- Any dosing interruption due to drug-related toxicity lasting $>$ 8 weeks

5.4.5 Detailed management algorithms for immune-oncology drug-related adverse events (including gastrointestinal, renal, pulmonary, hepatic, endocrine, skin and neurological) are provided in Table 4 below. These general guidelines constitute guidance to the Investigator and may be supplemented by discussions with the PI and IND Office in specific cases.

Since IO-agent/s stimulates the immune system, immune-related AEs (irAEs) may occur. Treatment of irAEs is mainly dependent upon severity (NCI-CTCAE grade): Grade 1 to 2: treat symptomatically or with moderate dose steroids, more frequent

monitoring

Grade 1 to 2 (persistent): manage similar to high grade AE (Grade 3 to 4)

Grade 3 to 4: treat with high dose corticosteroids

Table 4. Management of Immune-Related Adverse Events (irAEs) (These are to be followed for toxicities with all immune agents included in this protocol including immune checkpoints and monoclonal antibodies)

Gastrointestinal irAEs		
Severity of Diarrhea / Colitis (NCI-CTCAE v4.03)	Management	Follow-up
Grade 1 Diarrhea: < 4 stools/day over Baseline Colitis: asymptomatic	Continue IO therapy/s Symptomatic treatment (for example, loperamide)	Close monitoring for worsening symptoms Educate subject to report worsening immediately If worsens: Treat as Grade 2 or 3/4

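### Sections 5.4.3, 5.4.4 and 5.4.5 with Table 4 give different instructions for persistent or recurrent Grade 2 events on the IO agent, and none is said to govern

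*Combined protocol and SAP*

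**What the plan says.** **Section 5.4.3 (dose delay).** The delay rule exempts two kinds of Grade 2 event: "Grade 2 fatigue or laboratory abnormalities do not require delay". The laboratory exemption has limits. In stated ranges of ALT/AST, bilirubin and creatinine, patients "should have avelumab treatment withheld". A skin event triggers delay only at Grade 3. On restarting, "Subjects may resume treatment in the presence of Grade 2 drug-related fatigue", and patients with no Grade 3 drug-related skin event "may resume treatment in the presence of Grade 2 skin toxicity". Gut and lung events are treated differently: "Drug-related pulmonary toxicity, diarrhea, or colitis, must have resolved to baseline or at least" Grade 1.

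**Section 5.4.4 (discontinuation).** The Grade 2 rules open with "Any Grade 2 drug-related AEs should be managed as follows". If by cycle end the event is not at Grade 1 or lower, "infusions should not be given on the following cycle. If at the end of the following cycle the event has not resolved to Grade 1", IO treatment ends for good. The only event type excepted in this rule is hormone insufficiency manageable by replacement. Infusion reactions, hypersensitivity and tumor lysis are sent to separate guidance. A further rule begins "Upon the second occurrence of the same Grade 2 AE" and leads to permanent discontinuation, except for hormone insufficiency, or where the patient is benefiting and the investigator documents the discussion.

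**Section 5.4.5 and Table 4.** The lead-in says persistent Grade 1–2 immune-related events are managed like Grade 3–4 events. In the table, Grade 1–2 rash is first treated through. If it persists or recurs, the agent is delayed and resumed once the rash is improving. Grade 2 diarrhea that persists or recurs is given steroids, and the agent is resumed at Grade 1. Diarrhea that does not respond to steroids moves to the Grade 3–4 row, where the agent is discontinued.

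**The concern.** Section 5.4.4 contains its own delay rule (omit the next cycle), so it does not simply take over where 5.4.3 ends. Both sections address the same patient on the same day. Someone with drug-related Grade 2 fatigue on the last day of cycle 1 may be dosed in cycle 2 under one section and must not be under the other.

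Arms C and D are the open avelumab arms, planned at 24 patients each in Table 1. Both are judged on CRc within 3 months of starting therapy. The amount of avelumab a patient receives inside that window, and whether the patient counts as having stopped it for toxicity, can depend on which section the treating physician follows. Section 9.3 lists noncompliance with interruption and discontinuation criteria among the classes of violation or deviation, so either choice could be recorded as one.

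**Working it through.** The plan states no figure to reproduce. The check compares the instructions event by event and then counts doses.

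| Grade 2 drug-related event | 5.4.3 | 5.4.4 | 5.4.5 / Table 4 | Agree? |
|---|---|---|---|---|
| Persistent fatigue | No delay; may resume at Grade 2 | Omit next cycle; stop if unresolved at its end | No row | No |
| Persistent laboratory change outside the listed ranges | No delay | As above | No general row | No |
| Persistent skin toxicity, no Grade 3 skin event | No delay trigger at Grade 2; may resume at Grade 2 | As above | Table: delay, resume once improving. Lead-in: manage like Grade 3–4 | No |
| Persistent diarrhea | Delay; resume at baseline or Grade 1 or lower | May continue if Grade 1 or lower by cycle end; otherwise omit, then stop | Delay; resume at Grade 1; steroid failure goes to the Grade 3–4 row | Largely |
| Second occurrence, diarrhea | No separate rule | Stop unless benefiting | Steroids; resume at Grade 1 | No |
| Second occurrence, rash | No separate rule | Stop unless benefiting | Delay; resume once improving | No |

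**Precedence.** The one cross-reference in 5.4.3 to the discontinuation section is attached to delays of more than 8 weeks from unresolved Grade 3 or higher events. It does not reach Grade 2 events. The title of Table 4 says its rules are to be followed, while the text of 5.4.5 calls them guidance.

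**Dose count for Arms C and D.** Inputs: avelumab on Days 1 and 14 of each 28-day cycle (section 5.2), and a 3-month CRc window (section 11.0), taken as three cycles (3 × 28 = 84 days). Scheduled infusions: 2 × 3 = 6. Assume a Grade 2 fatigue, skin or qualifying laboratory event that starts in cycle 1 after both doses, with no other reason to interrupt.

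- Under 5.4.3, whether or not the event resolves: up to 2 + 2 + 2 = 6 of 6.
- Under 5.4.4, never resolving: 2 + 0 + 0 = 2 of 6, and none afterwards.
- Under 5.4.4, resolving to Grade 1 during cycle 2: 2 + 0 + 2 = 4 of 6.
- Under 5.4.4, resolving by the end of cycle 1: 2 + 2 + 2 = 6 of 6, so no difference.

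For persistent rash, the count of 6 holds under 5.4.3 read alone. Table 4 would delay, by an amount that depends on when the rash improves. The second-occurrence rule works differently: it omits no cycle first and goes straight to discontinuation, subject to the benefit exception.

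**The case against.** The strongest reply is that these rules leave room for judgment. Sections 5.4.3 and 5.4.4 are both limited to clinically significant drug-related events, 5.4.3 explicitly in the investigator's opinion. Section 5.4.5 describes Table 4 as guidance, and 5.4.7.3 allows other interruptions and modifications after discussion with the principal investigator. This softens the conflict in practice. It does not remove it: the significance qualifier sits in both sections and so cannot separate them, and case-by-case discretion sets no default.

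A second reply is that the sections agree more than they seem to. That is right for persistent diarrhea, where all three places require recovery to about Grade 1 before dosing. A reader might infer that 5.4.3 and Table 4 together form one permissive side against 5.4.4. The documents do not support that: Table 4 delays persistent or recurrent rash, and the 5.4.5 lead-in points toward stricter handling of persistent events.

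A third reply is that no effect on the analysis has been shown. That also stands. Everyone who receives at least one dose stays in the efficacy and safety analyses, and nothing in the documents links the number of avelumab infusions to CRc.

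**Conclusion.** The conflict is real but limited. It covers persistent Grade 2 fatigue, skin toxicity and laboratory changes outside the listed ranges (5.4.3 against 5.4.4, with the 5.4.5 lead-in and Table 4 also differing on rash), and second occurrences of Grade 2 diarrhea or rash (5.4.4 against Table 4). For a persistent event, the difference in avelumab exposure over three cycles runs from none to 6 versus 2 infusions. The extreme requires onset in cycle 1 after both doses and no resolution.

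A reader might infer that such patients generally receive a doublet from cycle 2 onward. That is only the worst case, since 5.4.4 lets dosing return once the event resolves. A reader might also try to put a number on affected patients, for example from the 28.9% fatigue figure in section 2.3.6. That figure is for any grade, in a study of venetoclax with a hypomethylating agent and no avelumab. The 12% Grade 2 immune toxicity in section 2.5 is for nivolumab. Neither describes persistence, so no count per arm can be given. Nor do the documents support a claim that the CRc estimate or a stopping boundary would change.

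**What to change.** Reconcile 5.4.3, 5.4.4, the 5.4.5 lead-in and Table 4 so that each of these has one instruction: persistent Grade 2 fatigue, persistent Grade 2 skin toxicity, persistent Grade 2 laboratory changes, and recurrent Grade 2 events. Add a sentence saying which section governs if they still differ. Which clinical rule applies is for the sponsor to decide.

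In the analysis section, add a summary by arm of avelumab infusions received in cycles 1–3, so that a reader can see how much of the planned triplet was delivered within the CRc window.

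The cost is an amendment to the wording and one descriptive table. Infusion dates would normally be recorded, but the documents do not say so explicitly, so the sponsor should confirm that the case report form holds them.

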5.4.6 Venetoclax specific dietary recommendations, concomitant medications and dose adjustments

Patients should not consume grapefruit or grapefruit products, Seville oranges, or Star fruit during treatment with venetoclax due to possible CYP3A mediated metabolic interaction.

Moderate and strong CYP3A inducers and inhibitors are discouraged during venetoclax administration. If a patient requires use of CYP3A inducers, use with caution. In many instances, such as antifungal prophylaxis with “azole” therapy in neutropenic patients, CYP3A inhibitors are required in AML patients. Venetoclax should be administered at

50% dose reduction in the setting of moderate CYP3A inhibitors (e.g. isavuconazole, ciprofloxacin, diltiazem) and 50-75% dose reduction in the setting of strong CYP3A inhibitors (e.g. posaconazole, voriconazole). The venetoclax dose reduction should continue for the duration of co-administration. In the event the co-administered CYP3A inhibitor is discontinued, the assigned venetoclax dose should be resumed 3 days after discontinuation. During the venetoclax ramp-up, these agents must be held; however, they may be started or resumed 24 hours after the highest planned dose of venetoclax is given, along with the appropriate dose reduction of venetoclax as above.

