- In Study M14-358 the ORR for AML subjects (given venetoclax plus azacitidine or decitabine) was 68%.¹⁰⁰
- In Study M14-387 the ORR for AML subjects (given venetoclax plus low dose arac-C) was 75%.¹⁰¹

Venetoclax Clinical Pharmacology and Pharmacokinetics: Venetoclax clinical pharmacology is being evaluated in several Phase I to III clinical trials, and data are available from three Phase I studies (M12-175, M13-367, M12-630), four Phase Ib

studies (M13-365, M12-901, GO29440, GP28331), one Phase II study (M14-212) and five dedicated clinical pharmacology studies (Study M13-364, M14-497, M13-363, M14-253 and M15-101).

In the Phase 1 Study M14-358, preliminary pharmacokinetic results in 31 treatment-naïve AML subjects were available for venetoclax doses ranging from 400 mg to 800 mg when given in combination with decitabine (Arm A) or azacitidine (Arm B) and with or without posaconazole (Arm C). For Arm A and Arm B, venetoclax steady-state mean Cmax and AUC₂₄ (Cycle 2 Day 5) ranged from 1.77 – 3.36 µg/mL and 24.7 – 59.5 µg/mL, respectively. Based on the limited preliminary pharmacokinetic data, there was no evidence to suggest a marked effect of the co-administration of decitabine and azacitidine on the pharmacokinetics of venetoclax. In Arm C of this study, preliminary pharmacokinetic results from 6 subjects were available on Cycle 1 Day 20 (venetoclax 400 mg alone QD until Day 20) and Cycle 1 Day 28 (venetoclax 100 mg QD with posaconazole given from Day 21 to Day 28). Venetoclax Cmax and AUC following co-administration of venetoclax 100 mg with posaconazole were 2.1- and 2.7-fold higher respectively, compared to venetoclax 400 mg alone.

Preliminary pharmacokinetic results of venetoclax are available from 12 treatment-naïve subjects with AML in Cohorts 1 (600 mg) and 2 (800 mg) from the ongoing Phase 1 combination study of venetoclax and low dose cytarabine (Study M14-387). On Cycle 1 Day 10 (with cytarabine), venetoclax mean Cmax and AUC₂₄ values ranged from 2.25 – 2.56 µg/mL and 34.7 – 44.6 µg·hr/mL, respectively. On Cycle 1 Day 18 (venetoclax alone), mean Cmax and AUC values of venetoclax ranged from 2.38 – 2.89 µg/mL and 37.9 – 45.3 µg·hr /mL. Dose-normalized Cmax and AUC₂₄ of venetoclax on Cycle 1 Day 10 (with cytarabine) were comparable to dose normalized Cmax and AUC₂₄ on Cycle 1 Day 18 (venetoclax alone), suggesting that co-administration of cytarabine did not markedly affect venetoclax exposures.

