As of 09 March 2016, a total of 45 subjects ≥ 65 years of age with treatment naïve AML ineligible to receive standard induction therapy were enrolled into the escalation stage at 3 dose levels of venetoclax at 400 mg, 800 mg, and 1200 mg. Venetoclax was administered daily during the 28-day cycles in combination with decitabine (20 mg/m² intravenously on Days 1 – 5 once every 28 days) or azacitidine (75 mg/m² intravenously or subcutaneously on Days 1 – 7 once every 28 days). Preliminary safety and efficacy data are available from the ongoing dose escalation stage of this trial.^{101,103}

The most common adverse events for all subjects in Study M14-358 were nausea (53.3%), diarrhea (44.4%), febrile neutropenia (40.0%), neutrophil count decreased (31.1%), platelet count decreased, cough, and fatigue (28.9% each), edema peripheral and hypokalemia (26.7% each). Events grade 3 and above were reported for the majority (91.1%) of subjects; the most common event was febrile neutropenia (40.0%). Serious adverse events were reported for 27 (60.0%) subjects, including febrile neutropenia (11 subjects), malignant neoplasm progression (3 subjects) atrial fibrillation, abdominal pain, non-cardiac chest pain, pyrexia, pneumonia, sepsis, bone pain (2 subjects each). All other events occurred in 1 subject each. The combination of venetoclax with decitabine and azacitidine demonstrates a tolerable safety profile.

As of 09 March 2016, the ORR, as assessed by the investigators for the subjects enrolled into the 3 dose levels, was 62.2% (28 of 45), with CR in 12 (26.7%), CRi in 15 (33.3%), and PR in 1 (2.2%). Four subjects (8.9%) were reported to have morphologic leukemia-free state (less than 5% blasts in bone marrow aspirate sample with at least 200 nucleated cells) after completion of Cycle 1. Eight patients (17.8%) had resistant disease. However, all of the patients with resistant disease had evidence of blast reduction at completion of Cycle 1. The patients enrolled into the 1200 mg dose level had a shorter follow-up at the time of this analysis.

The maximum tolerated dose has not been reached in either arm and dose escalation stage has completed enrollment. Enrollment into safety expansion at 400 mg and 800 mg dose of venetoclax in combination with both HMAs is ongoing.

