Venetoclax plus HMA in older patients with newly diagnosed AML: An ongoing phase Ib study has reporting promising safety and efficacy of venetoclax in combination with either azacitidine or decitabine in patients ≥ 65 years of age with previously untreated AML and who are ineligible for chemotherapy.^{113,114} At the most recent update, 145 patients were treated with a median age of 74 years (range, 65-86 years). Cytogenetics were poor risk in 49% of patients. The 30-day and 60-day mortality rates were 3% and 8%, respectively. Tumor lysis syndrome was not observed. The CR/CRi rate for the entire cohort was 66% with a median duration of CR/CRi of 11.0 months. The median overall survival for the entire cohort was 17.5 months. These results represent the best survival data for older, unfit patients with newly diagnosed AML yet reported. Emerging clinical and exposure response data have suggested that the 400mg dose of venetoclax has the best risk-benefit profile, and a phase III study of venetoclax 400mg with azacitidine in the frontline setting is ongoing.

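### Section 5.4.6 allows 200 mg venetoclax with posaconazole, although the protocol's own PK shows 100 mg with posaconazole already giving 2.7 times the AUC of 400 mg alone

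*Combined protocol and SAP*

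**What the plan says.** Venetoclax is given in Arms B and D. Section 5.2 ramps it over three days to a goal of 400 mg daily, and section 5.4.7.2 bars re-escalation above that dose.

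Section 5.4.6 discourages moderate and strong CYP3A inhibitors. It then says that in many instances, with azole prophylaxis during neutropenia as its example, "CYP3A inhibitors are required in AML patients". Two dosing rules follow:

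- Moderate inhibitors: "50% dose reduction in the setting of moderate CYP3A inhibitors (e.g. isavuconazole, ciprofloxacin, diltiazem".
- Strong inhibitors: "50-75% dose reduction in the setting of strong CYP3A inhibitors (e.g. posaconazole, voriconazole".

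No criterion is given for choosing within the second range. Inhibitors are held during ramp-up and may begin 24 hours after the highest planned dose.

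Three other statements bear on exposure:

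- Section 2.3.6 compares 100 mg with posaconazole against 400 mg without it in six subjects. Cmax and AUC "were 2.1- and 2.7-fold higher respectively, compared to venetoclax 400 mg alone".
- The same section describes a study of venetoclax plus an HMA "at 3 dose levels of venetoclax at 400 mg, 800 mg, and 1200 mg". It reached no MTD. It then states: "Enrollment into safety expansion at 400 mg and 800 mg dose of venetoclax in combination with both HMAs is ongoing".
- Section 2.6.4 reports that "exposure response data have suggested that the 400mg dose of venetoclax has the best risk-benefit profile".

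**The concern.** The lenient end of the strong-inhibitor range is 200 mg, which is also the moderate-inhibitor dose. For posaconazole, the strict end (100 mg) is the only one with data behind it in the protocol, and those data show it already overshooting the exposure of 400 mg alone. Doubling the dose can be expected to push exposure higher. No evidence is offered for 200 mg.

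What is at stake is venetoclax over-exposure in triplets that also contain GO (Arm B, up to 30 patients) or avelumab (Arm D, up to 24). A patient at the 400 mg goal on day 3 may start posaconazole about a day later, inside the 28-day DLT period. Table 11 strongly encourages prophylactic antifungals. The combination is therefore foreseeable, though its frequency is not stated.

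**Working it through.** **Stated figure.** The ratios of 2.7 (AUC) and 2.1 (Cmax) are reported results. They cannot be re-derived, because the protocol gives no concentrations for those six subjects and no measure of variability. I read 2.7-fold higher as a ratio of 2.7; an additive reading (3.7) would make the overshoot larger.

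**Permitted doses (sections 5.2 and 5.4.6).** 400 × (1 − 0.50) = 200 mg; 400 × (1 − 0.75) = 100 mg.

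**Interaction per mg, assuming dose proportionality.** AUC: 2.7 × 400/100 = 10.8. Cmax: 2.1 × 400/100 = 8.4. The dose with posaconazole that would match 400 mg alone is then 400/10.8 ≈ 37 mg by AUC, or 400/8.4 ≈ 48 mg by Cmax. Both lie below the permitted range.

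**Exposure at 200 mg with posaconazole, not measured.** Relative to 400 mg alone and with dose proportionality: AUC 2.7 × 200/100 = 5.4; Cmax 2.1 × 200/100 = 4.2. On the same scale, 1200 mg alone has an AUC of 1200/400 = 3.0, so 200 mg with posaconazole would be 5.4/3.0 = 1.8 times that.

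**Sensitivity to proportionality.** Let AUC vary as dose to the power b, with the same b with and without posaconazole. Values of b can be suggested from the AUC ranges in section 2.3.6, if the ends of each range belong to the lowest and highest doses, which the text does not say:

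- Low-dose cytarabine study, "subjects with AML in Cohorts 1 (600 mg) and 2 (800 mg) from the ongoing Phase 1 combination study": ln(44.6/34.7)/ln(800/600) = 0.87 and ln(45.3/37.9)/ln(800/600) = 0.62.
- HMA study, taking 400 and 800 mg as the ends and mixing two HMA arms: ln(59.5/24.7)/ln 2 = 1.27.

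I therefore use b from 0.6 to 1.3.

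| b | 200 mg + posaconazole vs 400 mg alone (2.7 × 2^b) | 200 mg + posaconazole vs 1200 mg alone (2.7 × (2/3)^b) | 100 mg + posaconazole vs 1200 mg alone (2.7/3^b) |
|---|---|---|---|
| 0.6 | 4.1 | 2.1 | 1.40 |
| 1.0 | 5.4 | 1.8 | 0.90 |
| 1.3 | 6.6 | 1.6 | 0.65 |

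Across this span the 200 mg end lies above the implied AUC of every dose in the HMA study. The 100 mg end lies between somewhat below and 40% above the implied AUC of the top dose.

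**The case against.** The strongest opposing case has five parts.

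1. **The label.** Venetoclax is commercial drug and the protocol appends its prescribing label, which is not in the public text and may set a narrower range. This stands as a limit. However, section 5.4.6 is the operative instruction and does not defer to the label for this dose.
2. **Latitude.** Strong inhibitors are discouraged, 200 mg is permitted rather than required, and isavuconazole is listed as moderate, so azole use need not mean posaconazole. All true; it limits how many patients are affected but supplies no support for 200 mg.
3. **Extrapolation.** Posaconazole was studied at one venetoclax dose, in six subjects. A reader might infer that 200 mg with posaconazole gives 2.7 times the AUC of 800 mg alone whatever the dose relation. That holds only if the dose exponent is the same with and without the inhibitor, and one inhibited dose cannot test this. The multiples at 200 mg are illustrations. The measured result at 100 mg is what carries the point.
4. **No demonstrated harm.** No MTD was reached through 1200 mg with an HMA, and the preference for 400 mg is a judgement of risk and benefit in newly diagnosed patients, not a toxicity ceiling. This also stands.
5. **Safeguards.** Inhibitors are held during ramp-up; venetoclax stops if the day-21 marrow shows remission or aplasia; later cycles give it on days 1–21 only; section 5.4.2 allows reduction to 200, 100 or 50 mg or a shorter course; and toxicity is monitored every three patients after the first six. These detect or limit harm after exposure. They do not justify the starting dose.

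**Conclusion.** The point holds in a limited form: the upper end of a permitted range has no support in the protocol and runs against the only PK the protocol cites. The firm part is that 100 mg with posaconazole gave 2.7 times the AUC and 2.1 times the Cmax of 400 mg alone, on preliminary data from six treatment-naive subjects. The figure of about 5.4 times at 200 mg rests on dose proportionality. Exceeding the AUC of 1200 mg rests on that assumption or on a common exponent of 0.6 to 1.3.

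A reader might infer that the rule is shown to be toxic, that most patients in Arms B and D will be over-exposed, or that the DLT and CRc results are compromised. The documents support none of these. They give no toxicity threshold, no rate of posaconazole use and no rate of choosing 200 mg. Section 3.4 requires DLTs to be assessed as unrelated to concomitant medications, which are documented each cycle (Table 13, footnote a). The evidence does not extend to voriconazole, for which no PK is given. This is a cheap patient-safety correction that should be made.

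**What to change.** In section 5.4.6, take posaconazole out of the 50–75% range and require a venetoclax reduction of at least 75% with it, so no more than 100 mg daily. This is one sentence, and 100 mg is already permitted by 5.4.6 and already a reduction level in section 5.4.2.

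The change does not restore the exposure of 400 mg alone. It keeps exposure nearer the range studied. The cost is less physician latitude. Under-dosing relative to 400 mg is unlikely on the protocol's figures: the posaconazole effect would have to be more than 2.7 times smaller than reported before 100 mg gave a lower AUC than 400 mg alone.

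Two minor additions do not affect the conclusion. Sections 5.6 and 7.2.12 limit CRF recording of concomitant medication to hydroxyurea; adding strong CYP3A inhibitors for Arms B and D is optional and would let toxicity and CRc be described by inhibitor use without returning to source records. Table 11 points to section 5.5.6, which does not exist; it should read 5.4.6.
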